4.2.1.4 Pharmacodynamic Endpoints

No pharmacodynamic endpoints will be evaluated in this study.

4.2.1.5 Planned Exploratory Biomarker Research

4.2.1.5.1 Planned Genetic Analysis

Genetic variation may impact a participant's response to therapy, susceptibility to, severity, and progression of disease. Variable response to therapy may be due to genetic determinants that impact drug ADME, mechanism of action of the drug, disease etiology, and/or molecular subtype of the disease being treated. Therefore, where local regulations and IRB/IEC allow, a sample will be collected for DNA analysis from consenting participants.

DNA samples may be used for research related to the study intervention(s), the disease under study, or related diseases. They may also be used to develop tests/assays including diagnostic

tests related to the disease under study, related diseases, and study intervention(s). Genetic research may consist of the analysis of 1 or more candidate genes, the analysis of genetic markers throughout the genome, or analysis of the entire genome. Analysis may be conducted if it is hypothesized that this may help further understand the clinical data.

The samples may be analyzed as part of a multistudy assessment of genetic factors involved in the response to understand study disease or related conditions.

4.2.1.6 Future Biomedical Research

The Sponsor will conduct FBR on DNA specimens for which consent was provided during this clinical study.

Such research is for biomarker testing to address emergent questions not described elsewhere in the protocol and will only be conducted on specimens from appropriately consented participants. The objective of collecting/retaining specimens for FBR is to explore and identify biomarkers that inform the scientific understanding of diseases and/or their therapeutic treatments. The overarching goal is to use such information to develop safer, more effective drugs/vaccines, and/or to ensure participants receive the correct dose of the correct drug/vaccine at the correct time. The details of FBR are presented in Appendix 6.

4.2.2 Rationale for the Use of Comparator/Placebo

Placebo will be used in this study to allow for an appropriate assessment of the safety data of oral MK-8189 and MK-5720 LAI and to maintain study blinding to reduce bias.

[figure not shown]
4.2.3 Rationale for Suicidal Ideation and Behavior Monitoring

Prospective assessment of suicidal ideation and behavior will be performed in this study using the C-SSRS. This assessment is being conducted in compliance with the 2012 FDA guidance requiring prospective assessment in clinical studies conducted under IND applications and studies that are intended for submission in a NDA to the Neurology or Psychiatry Divisions of the FDA or BLA, as well as assessment in studies that fall within the guidance for other reasons (eg, CNS active/penetrant compounds, and known mechanisms or indications for which suicidal ideation/behavior has been previously identified as a potential concern).

[figure not shown]
4.3 Justification for Dose

The methods used in calculating doses and estimated exposures are detailed in Section 4.3.1 and Section 4.3.2.

CCI

[figure not shown]

CCI

An oral tolerability run-in period with MK-8189 is included before administration of the IM MK-5720 injection. Due to the short half-life of oral MK-8189 (8-9 h), steady-state plasma exposures are likely to be achieved within the first two days following once daily administration of MK-8189. Hence, MK-8189 will be administered once-daily for 7 consecutive days in the oral-run in period to establish individual tolerability in participants at steady state prior to IM administration of MK-5720.

CCI

As this is a Phase 1 assessment of MK-5720 in humans, and the PK, pharmacodynamic and safety profiles of the compound are still being evaluated, modifications to the dose or dosing regimen may be required to achieve the scientific goals of the study objectives and/or to ensure appropriate safety monitoring of the study participants. Details of allowed modifications are provided in Section 8.10.6.

4.3.1 Starting Dose for This Study

The starting dose of 35 mg is proposed in conformance with the “Guideline on Strategies to Identify and Mitigate Risks for First-in- Human Clinical Trials with Investigational Medicinal Products” [European Medicines Agency 2007] as well as the MRSD calculation [Food and Drug Administration 2005], the MRSD for the first such instance of drug administration in humans is based on NOAEL determined in nonclinical safety studies performed in the most sensitive and relevant animal species adjusted with allometric scaling factors to calculate the HED.

A 4-week, 3-dose level toxicity study was conducted with MK-5720 in rats at (12, 30, 510 mg/kg/day) and rhesus (12, 36, 140 mg/kg/day) to assess the potential toxicity and toxicokinetic profile of MK-5720. No treatment related findings were identified in the GLP 1-month single dose IM toxicity studies with 3-month recovery period conducted with MK-5720 in rats and NHPs. Histological findings at the injection sites in rats and NHPs were consistent with those typically observed following administration of a long-acting formulation that produces an extended-release depot and the inflammatory response associated with MK-5720 histomorphology changes at the injection sites findings were resolved after a 3-month recovery period in both species.

The NOAELs for MK-5720 were the highest dose tested, 510 mg/kg in rats and 140 mg/kg in rhesus. While the NOAEL was the highest dose studied in both species in the 1-month GLP

compliant toxicological study, given the rat provides lower overall exposures for MK-5720 and lower EMs to the projected efficacious dose of MK-5720, rat is determined to be the most sensitive species. Therefore, rat NOAEL Cmax and AUC exposure cap for MK-5720 will be used for the purposes of safety multiple calculations that corresponds to 2.05 $\mu\text{M} \cdot \text{hr}$ and 0.0129 μM plasma exposures for AUC0-28d and Cmax respectively. See [Table 3] for PK exposures of MK-5720 at NOAEL doses in rats and rhesus.

Table 3 Pharmacokinetic Exposures of MK-5720 at NOAEL Doses

Species	Dose (mg/kg)	Cmax (μM)	AUC0-28d($\mu\text{M} \cdot \text{hr}$)
Rat	510	0.0129	2.05
Rhesus	140	0.0713	9.27

AUC0-28d= area under the concentration-time curve from 0 to 28 days, Cmax=maximum plasma concentration

The calculated HED corresponding to the rat NOAEL adjusted by using an allometric scaling factor is 4957 mg (510 mg/kg x 0.162 [rat to human dose conversion factor] x 60 kg [estimated human adult weight]). The MRSD calculated by applying a safety factor of 10, yields a starting dose of 495 mg. However, a safety factor of 50 has been applied to account for variability in the preclinical to clinical translation of input rate for the LAI. This results in a MRSD of 99 mg based on rat NOAEL (1/50*4957=99 mg) and 54 mg based on rhesus NOAEL (HED=140 mg/kg x 0.324 [rhesus to human dose conversion factor] x 60 kg=2722 mg; 1/50*2722 =54 mg).

The MK-5720 proposed starting dose of 35 mg provides a ~ 1.5- to 2.8-fold safety margin to the MRSD of 54 and 99 mg based on the rhesus and rat NOAEL, respectively. The lowest weight permitted in the study is 50 kg; even for a 50-kg participant the starting dose of 35 mg offers a 1.2-fold safety factor to the more conservative MRSD of 54 mg based on rhesus NOAEL. The 35-mg starting dose is also the lowest possible dose of the LAI that can be administered accurately via the IM route based on a 0.1-mL administration volume.

The starting dose of 35 mg is estimated to yield a human MK-5720 AUC0-28d of 0.09 $\mu\text{M} \cdot \text{hr}$ with a MK-5720 Cmax of 0.00019 μM that is approximately 23- and 68-fold lower than the rat AUC0-28d and Cmax NOAEL exposure cap and 103- and 375-fold lower than the rhesus AUC0-28d and Cmax NOAEL, respectively. CC1

For more detailed information regarding results from the rat and rhesus toxicological studies, please refer to the IB for MK-5720.

[figure not shown]
4.3.2 Maximum Dose Exposure for This Study

The maximum dose planned in this study is supported by the 4-week GLP repeat dose toxicity study with MK-5720 and also supported by clinical experience with MK-8189 across multiple Phase 1 and Phase 2 studies. As recommended by the EMA “Guideline on Strategies to Identify and Mitigate Risks for First in-Human Clinical Trials With Investigational Medicinal Products” [European Medicines Agency 2007], the maximum exposure in humans should be predefined and justified based on all available non clinical and clinical data, including PD, PK and findings in toxicity studies and exposures at the therapeutic dose range.

CCI

CCI

Administration of MK-5720IM injection of 12, 30, or 510 mg/kg and 12, 36 and 140 mg/kg of MK-5720 formulated as a LAI was administered as a single dose in rats and monkeys respectively, with a 1-month toxicity assessment and a 3-month treatment-free period to determine the potential toxicity and TK profile of MK-5720. The high-dose was selected to assess systemic toxicity at supratherapeutic exposures while the low and mid-dose were selected to assess local tolerability at relevant therapeutic exposures.

IM injection of MK-5720 LAI was generally well-tolerated at all doses (12, 30 and 510 mg/kg) in rats in the 1-month GLP toxicological study. There were no test article-related unscheduled deaths, and no test article-related changes in food consumption, ophthalmic, hematology, coagulation, serum biochemistry, or urinalysis parameters. There were no test article-related findings in other tissues of any rats in the 510 mg/kg group, indicating no systemic toxicity by the test article.

By the end of the 1-month toxicity assessment period, clinical signs (limited to injection site swelling) and body weight changes were generally resolved. Alterations in inflammatory biomarkers (A2M and AGP) were resolved and were not considered toxicologically meaningful. Chronic inflammation or a less pronounced change of local infiltrates at the intramuscular injection site observed at final necropsy (1 month after injection) in animals at ≥ 30 mg/kg was an expected finding typically observed with administration of long-acting formulations in rodents and had resolved in recovery animals necropsied approximately 4 months after dosing. The NOAEL was 510 mg/kg as injection sites reactions were not considered adverse at all dose levels, were reversible at the dose level examined (30 mg/kg)

and were consistent with findings typically observed after administration of long-acting injectable formulations to rats.

IM injection was considered to be generally well tolerated at all doses (12, 36 and 140 mg/kg) in monkeys in the 1-month GLP toxicological study. There were no test article-related unscheduled deaths, and no test article-related changes in body weight, ECG, ophthalmic, hematology, or urinalysis parameters. By the end of the 1-month toxicity assessment period at doses \leq 140 mg/kg, clinical signs had generally resolved and alterations in serum markers of inflammation (fibrinogen and C-reactive protein) were not considered toxicologically meaningful.

Minimal to moderate chronic inflammation at the IM injection site observed at final necropsy (1-month after injection) was an expected finding typically observed with administration of long-acting formulations in nonhuman primates. At the recovery sacrifice (limited to Cohort B animals in the low- and mid-dose groups), no test article-related gross or histomorphologic findings were observed at the injection site. No foci of chronic inflammation were observed in the quadriceps muscle group. Overall, the injection site reaction in the mid- and low-dose groups was considered to be in either a resolution phase or recovered after a 1-month toxicity assessment and a 3-month treatment-free period.

Based on the presence of test article-related findings at all dose levels, the NOAEL was 140 mg/ as injection sites reactions were not considered adverse, were reversible at the dose levels examined (12 and 36 mg/kg) and were consistent with findings typically observed after administration of long-acting injectable formulations to monkeys.

Since the rat NOAEL provides a \sim 1.4X EM for the AUC0-28d compared to 6.4X EM for the rhesus relative to the highest planned dose of 560 mg of MK-5720 based on the 1-month repeat dose toxicological studies, rat is considered the most sensitive species. Thus, the NOAEL for the purposes of establishing maximum allowable exposures is 2.05 μ M*hr and 0.0129 μ M for AUC0-28d and Cmax, respectively. The highest planned dose of 560 mg of MK-5720 [REDACTED] provides a 4.3-fold safety margin to the rat Cmax NOAEL exposure cap. Furthermore, no MK-5720-related effects on QTc or HR were noted in anesthetized NHPs up to the highest dose tested [REDACTED]

Maximal MK-5720 LAI single doses of up to 560 mg are proposed in the study to generate safety margins to the 280-mg dose of MK-572 [REDACTED]

Importantly, MK-5720 dose flexibility is built in the study as a contingency in the event resulting MK-8189 plasma concentrations from MK-5720 LAI are lower than that projected due to faster depletion of drug from the LAI or due to differences in LAI input rate observed in the clinic compared to that observed preclinically resulting in sub-efficacious MK-8189 plasma concentrations. MK-5720 LAI doses in the study have been selected in the study to result in MK-8189 plasma concentrations that remain within the clinical experience generated with the oral MK-8189 program in participants with schizophrenia and supported

by having sufficient safety margins at the highest dose proposed based on preclinical safety data generated with MK-5720 and MK-8189.

CCI

The projected MK-5720 exposures corresponding to the highest planned dose of 560 mg of MK-5720 LAI CCI provides a 4.3 and 1.4-fold safety margin to the rat (more sensitive compared to rhesus) MK-5720 C_{max} and AUC NOAEL exposure cap [refer to Section 4.3.1.2 of MK-5720 IB]. Furthermore, the projected MK-8189 C_{max} and AUC_{0-28d} corresponding to the 560 mg-dose of MK-5720 LAI CCI CCI provides a ~15 and 2.5-fold safety margin to the rat MK-8189 C_{max} and AUC NOAEL and ~ 9 and 3.3-fold to the rhesus C_{max} and NOAEL exposure cap, based on the 6 and 9-month repeat dose GLP tox study conducted with oral MK-8189 [refer to Section 4.3.2 of MK-5720 IB]. The projected MK-8189 C_{max} exposures corresponding to the 560- mg dose of LAI (~ 3 μ M) is within the range of the highest MK-8189 mean C_{max} exposure observed with 80-mg dose of oral MK-8189 on Day 2 of ~ 2.63 μ M (95% CI 2.08, 3.32 μ M; preliminary data) that was generally well tolerated in participants with schizophrenia (P014).

Because studies in preclinical species are not always predictive of what may occur in humans, safety of MK-5720 will be assessed throughout the study by monitoring AEs, physical/neurological examinations, VS, ECGs, and laboratory safety tests (chemistry, hematology, urinalysis). The timing of the safety endpoints has been planned to ensure adequate safety monitoring throughout the treatment period, taking into consideration the range of potential t_{1/2} predictions of MK-5720. Participants will be followed for at least 55 days to allow for adequate MK-5720 washout (~ 5-half-lives based on an estimated t_{1/2} of 10 days for MK-8189 in humans). Safety data from each dosing period will be carefully reviewed before escalation to the next higher dose. Key safety data such as VS, 12-lead ECGs, lab safety tests and physical/neurological examinations will be reviewed for up to at least 14 days postdose (Panel A) and up to 28 days postdose for all other panels prior to dose escalation to the next higher dose level. Plasma concentrations of MK-5720 from the preceding panels will be determined at the allocated PK breaks to ensure that the NOAEL AUC exposure limits are not exceeded at the doses in the subsequent panels. Since this is the first instance of administration of MK-5720 to humans, the dose levels and interval between doses may be adjusted based on safety and/or PK data from the prior periods.

4.3.3 Rationale for Dose Interval and Study Design

MK-5720, prodrug of MK-8189, a PDE10A inhibitor, is not considered a compound that can pose a potential safety risk to participants and is not a biological molecule and does not exhibit species-specific action and is not directed towards immune system targets. MK-5720 is approximately 650-fold less potent compared to MK-8189 based on in-vitro binding assay (MK-5720 PDE10 IC50 of 18.7 nM vs. 0.029 nM for MK-8189) and furthermore, due to the rapid bioconversion of MK-5720 to MK-8189 in vivo, MK-5720 concentrations anticipated in the clinic should be well below pharmacologically active concentrations and therefore, the main pharmacological activity expected in the clinic is a result of the MK-8189 metabolite. Furthermore, concentrations of MK-5720 will be monitored in the clinic so as not to exceed the NOAEL AUC0-28d and Cmax exposure cap.

The study design consists of 6 sequential panels (Panels A to F) and 3 PK breaks between Panels B to C, C to D, and E to F, respectively. In each treatment period for each panel of the study, participants will be randomized to receive MK-8189/MK-5720 (n=6 to 9) or placebo (n=2 to 3) in a blinded manner. All participants in a given panel shall receive the treatment or placebo on the same day in time spaced intervals based on Phase 1 clinical research standards for compounds not considered to be of high risk of harm. An oral tolerability run-in period with MK-8189 is incorporated in the study to [REDACTED]

[REDACTED] A washout period of at least 72 hours is included between the MK-8189 oral run-in period (Period 1) and the MK-5720 IM administration (Period 2) to fully understand the release kinetics and pharmacokinetics of MK-8189 following IM injection of MK-5720 in the absence of circulating carry-over MK-8189 from the prior oral run-in-period.

The dosing regimen was determined based on the following: clinical safety experience with MK-8189, the presence of preclinical safety margins for both MK-5720 and MK-8189, the inclusion of extensive safety monitoring in the clinic, and the fact that MK-5720 is not considered a compound with a high potential for risk of harm. There will be frequent, careful assessments of AEs throughout the postdose period. This recommendation is in keeping with the projected safety profile and the ability of the Phase 1 unit to monitor each participant closely. Safety data will be reviewed for at least up to 14 days post dose for dose escalation to Panel B and up to 28 days postdose for all subsequent panels before dose escalation between panels to allow for review of key safety parameters. The 14-day safety review period will allow for peak plasma concentrations of MK-8189 to be achieved from the MK-5720 LAI. Participants will be followed for at least 55 days allowing for collection of ~ 5 half-lives of MK-8189 based on estimated half-life of ~ 10 days in humans for MK-8189 from MK-5720 LAI.

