1.2 Schema

The study design is depicted in [Table 1] and [Figure 1].

Table 1 Dose Escalation Scheme

Panels ^{a,b}	MK-8189 Oral Run-In Dose ^c (Period 1)	Dose Escalation of MK-5720 (Period 2)									
		PK Break ^e			PK Break ^e			PK Break ^e			PK Break ^e
A	4 mg	35 mg ^d									
B	8 mg			70 mg ^d							
C	≤16 mg				≤140 mg ^d						
D	≤24 mg						≤280 mg ^{f,g}				
E	≤48 mg								≤560 mg ^{f,g}		
F	≤48 mg									≤560 mg ^{f,g}	

IM=intramuscular; LAI= long acting injectable; MRI=magnetic resonance imaging; PK=pharmacokinetics

Note: During Period 1, MK-8189 will be administered once daily for 7 days followed by a washout period of at least 72 hours prior to dosing MK-5720.

^a The suggested doses (with the exception of the starting dose) may be adjusted downward based on evaluation of safety, tolerability and PK data observed in previous intervention panels. Refer to Section 6.6 (Dose Modification) for the safety and PK data that will be reviewed prior to dose escalation.

^b Panels A to B, 6 participants will be randomized to receive MK-5720 and 2 participants to receive matching placebo. Panels C to F, 9 participants will be randomized to receive MK-5720 and 3 participants to receive matching placebo. Patients will be randomized according to a computer-generated allocation schedule.

^c The dose of MK-8189 during the oral run-in period may be adjusted downward based on the corresponding dose of MK-5720 administered in the panel to match steady state peak plasma exposures of MK-8189 from oral MK-8189 and MK-5720 IM injection.

^d MK-5720 LAI will be administered IM in the deltoid muscle

[figure not shown]
^e There will be a PK break following Panel B, C, D, and E

^f MK-5720 LAI will be administered IM in the deltoid, or the gluteal muscle based on PK from Panels A to C

[figure not shown]
^g MRI imaging shall be performed in panels at or 1 dose level below the highest dose of MK-5720 administered IM in the deltoid and gluteal muscle

Figure 1 Overall Study Design

Period 1: MK-8189 Oral Run-In

Period 2: MK-5720 Treatment Period

MRI=Magnetic resonance imaging; PK=pharmacokinetic

^aParticipants not currently being treated with antipsychotic medication may be domiciled minimally starting on Day -2 in Period 1.

^bThe washout period for MK-8189 will be ≥ 72 hours.

^cStudy Day is relative to dosing of study drug for each study drug.

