MRI exam will be incorporated in 2 panels at or 1 dose level below the highest dose of MK-5720 LAI that are administered IM in the deltoid and gluteal muscles to visualize the injection site depot using multislice spin-echo T2-weighted and assess the location of the depot in the muscle and to quantify drug depot characteristics, including volume and surface area over time. This information will be utilized to better understand any differences in PK between patients and to build models to better predict human PK from preclinical animal models in subsequent clinical studies.

Decision to dose participants with MK-5720 in any given panel will be based on demonstrating acceptable tolerability in individual participants with oral MK-8189 from the oral tolerability run-in period and based on key safety variables including AEs, VS, 12-lead ECGs, laboratory safety tests, neurological and physical examinations, and C-SSRS. The decision for a participant to proceed to Period 2 will be a joint decision between the PI and the Sponsor. Dose escalation decisions for MK-5720 will be based on key safety variables including AEs, VS, 12-lead ECGs, laboratory safety tests, neurological and physical examinations, C-SSRS, and local and systemic reactions assessed in Period 2. The decision to proceed to the next higher dose level will be based upon acceptable safety of MK-5720 at the previous dose. When available, plasma PK data will be reviewed to aid dose escalation decisions. For dose escalation to Panel B, the decision to proceed will be based on 14 days of safety and tolerability data from Panel A. ^{CCI} [REDACTED]

[REDACTED] Plasma concentrations of MK-5720 from the preceding panels will be determined at the allocated PK breaks to ensure that the NOAEL AUC exposure limits are not exceeded at the doses in the subsequent panels. Similarly, plasma concentrations of MK-8189 from the preceding panels will also be determined at the allocated PK breaks to ensure that MK-8189 exposures do not exceed exposures observed with oral MK-8189 at doses that are generally well tolerated in participants with schizophrenia. Dose escalation decisions for Panels C through F will be informed by safety, tolerability, and PK data from all patients in the prior panel through 28 days postdose.

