4.2.1.2 Safety Endpoints

No treatment related findings were identified in the GLP 1-month single dose IM toxicity studies with 3-month recovery period conducted with MK-5720 in rats and NHPs. The

NOAELs were the highest dose tested, 510 mg/kg in rats [REDACTED]

[REDACTED] for MK-5720.

Clinical pathology changes were not considered toxicologically meaningful, given the small magnitude and transient nature, and were attributed to an inflammatory response associated with MK-5720 histomorphology changes in the injection sites noted in rats at ≥ 30 mg/kg [REDACTED]

[REDACTED] In both species these findings resolved after a 3-month recovery period. Histological findings at the injection sites in rats and NHPs were consistent with those typically observed following administration of a long-acting formulation that produces an extended-release depot [Paquette SM, et al 2014].

Because studies in preclinical species are not always predictive of what may occur in humans, the safety and tolerability of MK-5720 will be assessed throughout the study by monitoring participants frequently for clinical AEs as well as through the conduct of neurological exams, physical exams, ECGs, VS, and laboratory safety tests (chemistry, hematology, urinalysis). The timing of the safety endpoints has been planned to ensure adequate safety monitoring throughout the treatment period also taking into consideration the range of potential half-life predictions of MK-8189 from the MK-5720 LAI. Key safety data such as VS, 12-lead ECGs, lab safety tests and physical/neurological examinations will be reviewed for up to at least 14-days postdose for Panel A prior to dose escalation to Panel B and up to 28-days postdose prior to dose escalation to the next higher dose level in all other treatment periods. The C-SSRS will be administered to monitor mood and suicidal ideation and behavior in all trial participants (see Section 4.2). In addition, scales will be included to evaluate EPS and general well-being.

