4.2.1.3 Pharmacokinetic Endpoints

One of the primary objectives of the study is to characterize the PK profile of MK-5720 as well as MK-8189 as rising single doses of administration of the IM MK-5720 LAI in Period 2. In order to characterize the PK profile of MK-5720 and MK-8189, noncompartmental PK parameters, AUC0-last (MK-5720 only), AUC0-inf, AUC0-28d (MK-8189 only), Cmax, C28d (MK-8189 only), Tmax, apparent t1/2, apparent CL/F, and apparent Vz/F will be estimated after single-dose IM administration of the MK-5720 LAI. The dose escalation criteria based on PK analysis are listed below in [Table 2]. Additionally, in Period 1 of the study, one of the exploratory objectives is to characterize the PK profile of MK-8189 following multiple oral doses of MK-8189. Therefore, the noncompartmental PK parameters, AUC0-24, Cmax, Tmax, terminal t1/2 and C24 will be estimated on day 1 and day 7. Plasma samples will be analyzed based on prespecified time point sampling mentioned in Section 1.3.

Table 2 Dose Escalation Criteria Based on PK Analysis

Dose (Panel)	Dose Escalation Decision Criteria
140 mg (C)	28d postdose PK analysis from the preceding doses from Panels A and B
280 mg (D)	28d postdose PK analysis from the preceding dose in Panels C
≤560 mg (E)	28d postdose PK analysis from the preceding dose in Panel D
≤560 mg (F)	28d postdose PK analysis from the preceding dose in Panel E
28d=28 days; PK=pharmacokinetics	

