6.6 Dose Modification (Escalation)

All dose-escalation decisions will be made jointly by the investigator and the Sponsor. Members of the Sponsor safety review team will include: the trial clinical director, trial clinical scientist, senior level clinical director and trial biostatistician. Additional Sponsor attendees may include a clinical research associate and a pharmacologist. The Sponsor safety review team will obtain input from the investigator regarding his/her evaluation of safety and tolerability from the previous dosing period and his/her recommendation to dose escalate in the next panel.

Each dose-escalation decision will occur after at least 8 (Panels A and B) and 12 (Panels C through F) evaluable participants have completed the previous dose level (participants will be randomized to receive MK-5720 or placebo in a 3:1 ratio, respectively).

Dose-escalation decisions will be based on blinded key safety variables, with summary statistics as needed. Safety variables will include, vital signs, 12-lead ECG, laboratory safety tests, AE, and neurological assessments from the previous dose levels up to at least 14 days postdose. PK data may be included in the dose-escalation decisions (Section 2.1 and Section 2.2).

If, as judged by the Sponsor and investigator, the safety and tolerability data do not justify dose escalation, the dose will not be increased as planned. Instead, participants may:

- receive the same dose level to further explore safety and tolerability at that level,
- receive a lower dose of the study intervention (with or without food),
- receive the same or lower dose as a divided dose, or
- dosing may be stopped.

Participant discontinuation criteria are outlined in Section 7.

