8.10.6 Study Design/Dosing/Procedures Modifications Permitted Within Protocol Parameters

This is a Phase 1 assessment of MK-5720 in humans, and the PK, pharmacodynamic, and safety profiles of the compound are still being elucidated. This protocol is written with some flexibility to accommodate the inherent dynamic nature of Phase 1 clinical studies.

Modifications to the dose, dosing regimen, and/or clinical or laboratory procedures currently outlined may be required to achieve the scientific goals of the study objectives and/or to ensure appropriate safety monitoring of the study participants.

As such, some alterations from the currently outlined dose and/or dosing regimen may be permitted based on newly available data, but the maximum daily dose may not exceed those currently outlined in the protocol.

- Repeat of or decrease in the dose of the study intervention administered in any given panel
- Interchange of doses between panels
- Entire panel(s) may be omitted
- Remove a planned PK pause if agreed by Sponsor and investigator if no further increases in total daily dose

- Addition of PK pause
- Modification of the PK sample processing and shipping details based on newly available data

The PK sampling scheme currently outlined in the protocol may be modified during the study based on newly available PK data (eg, to obtain data closer to the time of peak plasma concentrations). If indicated, these collected samples may also be assayed in an exploratory manner for metabolites and/or additional pharmacodynamic markers.

Up to additional 50 mL of blood may be drawn for safety, PK, and/or pharmacodynamic analyses. The total blood volume withdrawn from any single participant will not exceed the maximum allowable volume during his/her participation in the entire study (Appendix 8).

The timing of procedures for assessment of safety procedures (eg, vital signs, ECG, safety laboratory tests, etc.) may be modified during the study based on newly available data. Additional laboratory safety tests may be added to blood samples previously drawn to obtain additional safety information. These changes will not increase the number of study procedures for a given participant during his/her participation in the entire study.

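### Section 4.3.3 omits the PK break before the 280 to 560 mg step that Tables 1 and 2 set, and Section 6.6 allows every escalation on 14 days of safety data with PK optional

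*Combined protocol and SAP*

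**What the plan says.** On the number of PK breaks:

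- Section 1.2, Table 1 note e: "There will be a PK break following Panel B, C, D, and E".
- Section 4.2.1.3, Table 2, row for Panel E: "28d postdose PK analysis from the preceding dose in Panel D".
- Section 4.3.3: "3 PK breaks between Panels B to C, C to D, and E to F".

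On the data needed to escalate:

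- Section 4.1: "Dose escalation decisions for Panels C through F will be informed by safety, tolerability, and PK data from all patients in the prior panel", with a 28-day window. For Panel B it asks for 14 days of safety and tolerability data from Panel A. A separate sentence makes PK review conditional on the data being available.
- Section 4.2.1.2 sets at least 14 days for Panel A and, for the rest, "up to 28-days postdose prior to dose escalation to the next higher dose level". Sections 4.3.2 and 4.3.3 make the same split.
- Section 6.6 makes no distinction between panels. Its safety variables run through "neurological assessments from the previous dose levels up to at least 14 days postdose", and "PK data may be included in the dose-escalation decisions (Section 2.1 and Section 2.2"). Those two sections are the Study Rationale and the Background; neither sets an escalation criterion.

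On dropping a break, Section 8.10.6 permits the team to "Remove a planned PK pause if agreed by Sponsor and investigator if no further increases in total daily dose".

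**The concern.** The break missing from Section 4.3.3 is the one before the last planned increase, where the dose can double and the projected margin is smallest. The section keeps the E to F break, where both panels share the same 560 mg ceiling. Section 8.10.6 would allow that break to be dropped. It would not allow the D to E break to be dropped at the planned doses, because the dose rises.

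Section 6.6 is where an escalation team will look for its rule. Read alone, it lets the team move from 280 to 560 mg on 14 days of safety data with no PK review, which would breach Table 2. Section 4.2 gives the reason this matters for a depot: once injected, daily exposure to MK-8189 cannot be reduced. The oral run-in tests each participant's tolerance of MK-8189 but gives no MK-5720, so it does not check the prodrug exposure to which the cap applies.

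**Working it through.** **1. PK breaks, step by step**

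| Step | Planned MK-5720 dose (mg) | Table 1 note e | Table 2: 28-day PK from | Section 4.3.3 |
|---|---|---|---|---|
| A to B | 35 to 70 | none | none | none |
| B to C | 70 to ≤140 | break | Panels A and B | break |
| C to D | ≤140 to ≤280 | break | Panel C | break |
| D to E | ≤280 to ≤560 | break | Panel D | **not listed** |
| E to F | ≤560 to ≤560 | break | Panel E | break |

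Table 1 has four breaks and Section 4.3.3 has three. The only difference is D to E.

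**2. Data required to escalate**

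| Source | A to B | Later steps |
|---|---|---|
| Section 4.1 | 14 days, safety | 28 days, safety and PK |
| Sections 4.2.1.2, 4.3.2, 4.3.3 | at least 14 days, safety | up to 28 days, safety |
| Section 6.6 | at least 14 days, safety; PK optional | the same as A to B |

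**3. Margin at each dose**

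Inputs: the projected MK-5720 AUC0-28d at 35 mg is 0.09 µM·hr and Cmax is 0.00019 µM (Section 4.3.1). The caps are 2.05 µM·hr and 0.0129 µM (Sections 4.3.1 and 4.3.2). The table of projected exposures at higher doses is not visible, so I assume exposure proportional to dose.

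Margin = cap ÷ (35 mg projection × dose/35).

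The plan's own figures first:

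- 35 mg: 2.05/0.09 = 22.8 and 0.0129/0.00019 = 67.9. The protocol prints about 23 and 68.
- 560 mg AUC: 2.05/(0.09 × 16) = 2.05/1.44 = 1.42. The protocol prints 1.4. Rounding of 0.09 allows 1.35 to 1.51.
- 560 mg Cmax: 0.0129/(0.00019 × 16) = 4.24. The protocol prints 4.3. Rounding of 0.00019 allows 4.13 to 4.36.

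Proportional scaling therefore agrees with the printed margins at both ends. In between:

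- 140 mg: 0.09 × 4 = 0.36; 2.05/0.36 = 5.7.
- 280 mg: 0.09 × 8 = 0.72; 2.05/0.72 = 2.85.

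**4. What a Panel D result could show**

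If doubling the dose doubles exposure, 560 mg reaches the cap when the Panel D mean is 2.05/2 = 1.025 µM·hr. That is 1.025/0.72 = 1.42 times its projection.

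**The case against.** **Section 6.6 forbids nothing that Table 2 asks for.** Fourteen days is a minimum, and a 28-day review meets it. Calling PK optional is accurate across all steps taken together, since A to B has no PK break. Section 6.6 also requires that 8 or 12 evaluable participants have completed the previous dose level. All of this stands. However, completion is not defined there, and the requirement supplies neither a 28-day window nor PK.

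**The stricter text is not uniformly firm.** Note e gives no duration. Sections 4.2.1.2, 4.3.2 and 4.3.3 say up to 28 days rather than at least 28. Section 4.1 contains the conditional PK sentence, and some text beside its Panel B rule is redacted. This also stands, and it is why Section 4.1 needs an edit too. Table 2 is nonetheless explicit for Panel E.

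**Panel C gives an early warning.** Under the same proportionality, 560 mg reaches the cap if the 140 mg mean is 2.05/4 = 0.5125, which is 0.5125/0.36 = 1.42 times projection. No section drops the PK break after Panel C. What Panel D adds is a check on proportionality itself, one doubling below the top dose.

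**The cap is not a toxicity threshold.** It is the exposure at the highest rat dose tested, without systemic toxicity.

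**Stronger readings that the documents do not support.**

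- A reader might infer that stopping rule 3 cannot work without complete 28-day Panel D data. Section 6.6.1 bases the rule on emerging mean data that point to a Cmax or AUC above the limit, so partial profiles can trigger it.
- A reader might infer that day-14 data could not reveal an excess. They are incomplete for an AUC0-28d but still informative: a Panel D AUC0-14d already above 1.025 would settle the matter.
- A reader might infer that escalation to 560 mg without PK is planned. Most of the text points the other way.

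**Conclusion.** The conflict over breaks is real and lies in the current text: Section 4.3.3 contradicts Table 1 note e and Table 2 on D to E. It looks like a drafting slip, because the section keeps the break that Section 8.10.6 would allow to be removed and loses the one it would not. Section 6.6 is a looser rule rather than a direct prohibition. It allows, at every step after A to B, an escalation that other sections would hold for 28-day data, and it cites the wrong sections.

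The gap falls where the projected AUC0-28d margin goes from about 2.8-fold to 1.4-fold. The 1.4 is the protocol's own figure; the 2.8 rests on dose proportionality. The intended rule can be recovered from Section 4.1 and Table 2, so this calls for alignment of wording and not for redesign. It should be done before the Panel E decision.

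**What to change.** 1. Section 4.3.3: state four PK breaks, between Panels B and C, C and D, D and E, and E and F.
2. Section 6.6: replace the single 14-day rule and the optional PK sentence with: *For escalation to Panel B, safety data from Panel A through at least 14 days postdose will be reviewed. For Panels C through F, safety data from the prior panel through 28 days postdose and the 28-day PK data specified in Table 2 (Panels A and B for Panel C; the preceding panel for Panels D to F) will be reviewed.* Refer to Section 4.1 and Table 2 in place of Sections 2.1 and 2.2.
3. Section 4.1: limit the sentence that makes PK review conditional on availability to the A to B decision.

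Section 8.10.6 can stay as it is.

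Cost: wording in three places. No visits, samples, participants or doses change. Section 4.1 and Table 2 already set the 28-day wait, so the planned timeline is unaffected. Compared with a literal 14-day reading of Section 6.6, each escalation after A to B takes up to 28 − 14 = 14 days longer.
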